### **Magnetic Resonance Spectroscopy (MRS) ψ:**

We will use MRS to quantify glutathione (GSH) and GABA levels in children with NF1 to assess effects of NAC therapy. This will allow for regional correlation between MRS and neuropsychometric outcomes. The HERMES MRS sequence (echo time 68 ms, repetition time 2000 ms) requires 11 minutes per 27 mL location of interest sampled in the brain. MRS is performed within the medial frontal cortex including dACC [78, 79]. MRS detects neurochemical concentrations within key neural elements (neurons, axons, glia) reflecting structural composition such as N-acetyl aspartate, creatine with phosphocreatine, total choline, and myo-inositol and functioning with glutamate, GSH and GABA. The HERMES method provides GSH, GABA and

GLX; the GABA-off and GSH-off portion of the HERMES experiment provides a spectrum for standard metabolites. MRS data are postprocessed with LCModel and Gannet software and adjusted for tissue composition and neurochemical relaxation, to produce concentrations.

**Table 4: Schedule of Assessments**

	Visit 1	Visit 2				Visit 3		Visit 4
	Screening	Baseline	Abbreviated Remote monitor and safety	Remote monitor and safety	Abbreviated Remote monitor and safety	End Intervention	Remote monitor and safety	Follow Up
Task	Week 0	Week 1	Week 2	Week 4	Week 6	Week 8	Week 10	Week 12
Review Eligibility Criteria $\Psi$	X							
KBIT-2 (Kaufman Brief Intelligence Test, Second Edition) $\Psi$	X							
KSADS (MedHis)	X							
Cognitive Function Screening $\Psi$	X							
Test dose	X							
Informed Consent $\Psi$	X							
Brain Imaging (MRI/MRS) $\Psi$		X				X		X
Urine Pregnancy (Females only)	X	X						
Vitals*		X				X		X
Safety labs*		X				X		X
Physical Exam*		X				X		X
ADHD-RS (DuPaul) $\Psi$		X		X		X	X	X
KSADS (CC)		X		X		X	X	X
PARS (Pediatric anxiety rating scale)		X		X		X	X	X
CDRS (Children's depression rating scale)	X	X		X		X	X	X
C-SSRS (Columbia Suicide Severity Rating Scale)	X	X		X		X	X	X
Wechsler Intelligence Scale for Children, Fifth Edition (WISC-V) $\Psi$	X	X				X		X
Behavioral Rating Inventory of Executive Function (BRIEF-2) $\Psi$		X				X		X
Test of Variables of Attention (TOVA) $\Psi$		X				X		X
PANESS scale $\Psi$		X				X		X
TMS assessment $\Psi$		X				X		X
NAC/Placebo Prescription		X						
Med Log		X	X	X	X	X	X	X
AE assessment (MedDRA)		X	X	X	X	X	X	X
Follow-up plan								X

\* Indicates clinical procedures performed as standard of care

$\Psi$  Indicates research procedures to be completed in both treatment and non-treatment cohorts

## **DATA ANALYSIS/METHODS:**

### **NAC Trial at CCHMC**

We propose performing a single center randomized double-blind placebo controlled, prospective, Phase II study to explore safety, tolerability, and efficacy of NAC on motor behavior and/or attention deficit in children with NF1 aged 8 through 16 years old.

**Determination of sample size:**

No data exist on the effects of NAC in children with NF1. Clinical improvement will be evaluated as a change score ( $\text{PANESS}_{\text{post-NAC}} - \text{PANESS}_{\text{baseline}}$ ). Those subjects whose severity PANESS score decreased by at least 20% from baseline to week 8 will be considered clinically meaningful. The sample size calculation was based on a two-sided t-test to detect the difference in change scores between two groups. We assume the PANESS score does not change for patients in placebo group. A sample size of 26 participants per group (52 in total) achieves 81% power to detect an effect size of 0.8 with significance level of 0.05 [80]. To allow for a 10% dropout rate prior to the 12-week point, a total of 58 participants will be enrolled.

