**Inclusion criteria :**

1. Male and females aged 8 - 16 years (up to 16 years and 6 months) at time of enrollment
2. Meets NIH diagnostic criteria for NF1
3. Abnormal PANESS study (score at or above the age/sex-based mean)
4. Participants must have a full-scale intelligence quotient (IQ) of 70 or above, as determined by neurocognitive testing within the last 3 years or during the enrollment process
5. Participants on stimulant or any other psychotropic medication should stay on a stable dose (no change in dose) for at least 30 days before entering the study. A stable dose should be maintained throughout the study until completion of all study visits.

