#### Randomization:

Following the screening period, each participant will be sequentially assigned to one of the 2 treatment groups: NAC or placebo. This randomization will be stratified to ensure balance of ADHD, ages and sexes between the intervention groups. Randomization will be implemented by the study statistician for this trial utilizing a permuted blocks approach. Password protection will be implemented to ensure that only certified clinical personnel are allowed to randomize patients and access the database. At the time

videoconference, and/or via electronic surveys such as REDCap. If determined to be eligible during the initial screen, the patient will enter the second phase of screening as outlined in the *Eligibility Verification* document.

After eligibility criteria are confirmed, the informed consent process will occur. Informed consent can take place in person, on the phone, via email, videoconference, and/or via electronic surveys such as REDCap. Following the consent process, eligibility screening will occur. The primary diagnostic screen will be the PANESS. Clinically administered PANESS scores performed within 90 days of enrollment can be used to confirm eligibility and as a baseline PANESS score for this study. Participants whom have not had a recent (within 90 days) PANESS assessment as a part of clinical care will be screened with PANESS. A set of behavioral and neuropsychometric assessments will be administered and families will be informed if they are eligible for the next phase of the study. The questionnaires are outlined in **Table 4**.

Parents/participants will deliver a teacher rating scale packet, with questionnaires/rating scales targeted to the classroom environment, to their child's teacher. Teachers will return completed rating scales to the study team via US mail using an addressed/stamped envelope provided by the study team. A letter will be included within the teacher packet indicating that, by completing the questionnaires and mailing them in, they provide implicit consent. Communication with teachers and distribution of surveys may occur digitally via REDCap, telephone, videoconference, and/or email.

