**Randomization:**

Following screening period, each participant will be sequentially assigned to one of the 2 treatment groups: NAC or placebo. This randomization will be stratified to ensure balance of sexes and ADHD between the intervention groups. Randomization will be implemented by the study statistician for this trial utilizing a permuted blocks approach. Password protection will be implemented to ensure that only certified clinical personnel are allowed to randomize patients and access the database. At the time of randomization, each participant will be assigned a unique medication kit identification number that will be used throughout the duration of the study.

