**Statistical analysis:**

All analysis will be performed with SAS software version 9.4 (SAS Institute Inc., Cary, NC, USA). Spearman's correlation coefficient will be used to evaluate the univariate association between primary outcome (improvement of PANESS scores) and other neurophysiology and brain imaging measurements. Multivariate linear regression model will be used to assess the correlation between the outcomes and the risk factors adjusting for all possible confounders. Model selection criterions such as stepwise method will be employed when necessary. A p-value less than 0.05 will be considered statistically significant.

1. We will assess behavior vs. neurophysiology correlations:

- 1) two-month PANESS change ( $\text{PANESS}_{\text{post-NAC}} - \text{PANESS}_{\text{baseline}}$ ) vs. SICI change ( $\text{SICI}_{\text{post-NAC}} - \text{SICI}_{\text{baseline}}$ ).
- 2) two-month DuPaul change ( $\text{DuPaul}_{\text{post-NAC}} - \text{DuPaul}_{\text{baseline}}$ ) vs. SICI change ( $\text{SICI}_{\text{post-NAC}} - \text{SICI}_{\text{baseline}}$ ).
- 3) two-month BRIEF change ( $\text{BRIEF}_{\text{post-NAC}} - \text{BRIEF}_{\text{baseline}}$ ) vs. SICI change ( $\text{SICI}_{\text{post-NAC}} - \text{SICI}_{\text{baseline}}$ ). Paired t test comparisons of single pulse TMS responses (resulting from pTMS) will be performed to test whether, at each session, single pulse TMS responses differed. The mean single pulse TMS responses for each individual constitute the denominators for the SICI and ICF ratios and need to remain consistent for changes in SICI to be interpretable.

2. We will assess primary behavior (PANESS) vs. neuroimaging correlations:

- 1) two-month PANESS change ( $\text{PANESS}_{\text{post-NAC}} - \text{PANESS}_{\text{baseline}}$ ) vs. Fraction Anisotropy (FA) change ( $\text{FA}_{\text{post-NAC}} - \text{FA}_{\text{baseline}}$ ).

2) two-month PANESS change ( $\text{PANESS}_{\text{post-NAC}} - \text{PANESS}_{\text{baseline}}$ ) vs. MRS GSH change ( $\text{GSH}_{\text{post-NAC}} - \text{GSH}_{\text{baseline}}$ ).

3) two-month PANESS change ( $\text{PANESS}_{\text{post-NAC}} - \text{PANESS}_{\text{baseline}}$ ) vs. MRS GABA change ( $\text{GABA}_{\text{post-NAC}} - \text{GABA}_{\text{baseline}}$ ). The current HERMES method data analysis of MRS can observe GSH concentration changes in the brain of over 20%. We will determine if NAC dose changes GSH in brain and correlates with the primary outcome of study (PANESS).

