For analyses of change over time, mixed models which include subject-specific random effects will be used to account for the correlation of multiple measurements on each subject and capture between-subject variation in rates of change. Unless otherwise noted, the Type I error rate for hypothesis tests and confidence intervals will be controlled at  $\alpha=0.05$ . To assist interpretation, the size of effects of interest in each model will be represented by  $R^2$  (proportion of outcome variation explained by predictors) for linear regression models and/or Cohen's  $d$  (difference in group means, in standard deviation units) for two sample t-tests [81].

Exploratory and descriptive data analysis will precede all inferential analyses to ensure that distributional assumptions are satisfied. In addition to computation of basic descriptive sample statistics (measures of central tendency, variability, and bivariate association), graphical tools such as histograms and scatterplots will be used to assess, e.g., approximate normality, linearity, and presence of influential outlying observations. If substantial violations of parametric assumptions are detected, we will implement non-parametric alternatives, including classical rank-based procedures as well as computationally-intensive sample re-use procedures such as the nonparametric bootstrap. Non-parametric procedures generally have less power than parametric procedures when the assumptions of the latter are met, but often have markedly better properties when the assumptions fail.

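### The primary NAC-versus-placebo analysis of PANESS is not written down, and adjustment for baseline and strata is not prespecified

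*Combined protocol and SAP*

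**What the plan says.** PANESS is the primary outcome (Specific Aim), and Determination of sample size defines it as a post-treatment minus baseline change score. That paragraph then says: "The sample size calculation was based on a two-sided t-test to detect the difference in change scores between two groups". This is a basis for sizing; no sentence says that it is also the planned analysis.

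The Statistical analysis section contains three further candidates:

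- Mixed models: "For analyses of change over time, mixed models which include subject-specific random effects will be used to account for the correlation of multiple measurements". No outcome, fixed effects, treatment term or week-8 contrast is listed.
- Two-sample t-tests, which appear only as the setting in which Cohen's d is reported: "difference in group means, in standard deviation units) for two sample t-tests".
- A regression: "Multivariate linear regression model will be used to assess the correlation between the outcomes and the risk factors adjusting for all possible confounders". It is followed by: "Model selection criterions such as stepwise method will be employed when necessary". The context is association between outcomes and risk factors, and no treatment term is named.

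On stratification, the Randomization section that follows the consent text says: "This randomization will be stratified to ensure balance of ADHD, ages and sexes between the intervention groups". The Randomization section under DATA ANALYSIS/METHODS says: "This randomization will be stratified to ensure balance of sexes and ADHD between the intervention groups". Age is a stratum in one and not in the other.

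**The concern.** A t-test on change, a mixed model of unspecified form and a covariate-adjusted regression would all be consistent with the text, and the choice could be made after the data are seen. With one primary endpoint and about 52 evaluable children, that choice should be closed in advance.

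There is also an efficiency point. Baseline PANESS, sex and ADHD status are collected for every randomised child. An unadjusted change-score test makes less than full use of baseline and ignores the factors used to balance the arms. If those factors predict change, an analysis that omits them after stratified randomisation is conservative. Because the two Randomization sections differ on age, even an analyst who meant to adjust for the strata could not tell from the plan which ones to use.

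**Working it through.** **Inputs from the plan (Determination of sample size).** 26 evaluable children per arm, effect size d = 0.8 in change-score SD units, two-sided α = 0.05, stated power 81%, 10% dropout, 58 enrolled.

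**Inputs assumed, because the documents do not give them.** Baseline-to-week-8 PANESS correlation r = 0.5, 0.7 or 0.9; share of change variance explained by the strata 0%, 10% or 20%; block size 4.

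**Step 1: the plan's own figure.** The noncentrality is 0.8 × √(26 × 26/52) = 0.8 × √13 = 2.884 on 50 degrees of freedom. Noncentral-t power is 80.7%, which agrees with 81%. Enrolment is 52/0.90 = 57.8, hence 58. The sizing is sound.

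**Step 2: baseline-adjusted analysis, equal variances at both visits.** The change score has variance 2σ²(1 − r) and the ANCOVA residual has variance σ²(1 − r²), so their ratio is (1 + r)/2. Power follows from an effect of 0.8/√ratio on 49 degrees of freedom.

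**Step 3: allowing for the entry criterion.** Inclusion requires: "Abnormal PANESS study (score at or above the age/sex-based mean". If a normal baseline is cut at its mean, its variance falls to 1 − 2/π = 0.363 of the full value. With r the untruncated correlation, the ratio becomes (1 − r²)/[(1 − r)² × 0.363 + (1 − r²)]. At r = 0.5 this is 0.75/(0.25 × 0.363 + 0.75) = 0.892.

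**Step 4: charging for the strata terms.** Trials with n = 52 were simulated (20,000 runs per scenario), with permuted blocks within sex by ADHD and strata that have no effect. ANCOVA was fitted on treatment, baseline, sex and ADHD (47 degrees of freedom). The results fall slightly below the formula because chance covariate imbalance is also paid for.

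| r (assumed) | Baseline | Variance ratio | Formula power | Simulated t-test | Simulated ANCOVA |
|---|---|---|---|---|---|
| 0.5 | equal variances | 0.75 | 90.4% | 80.3% | 89.5% |
| 0.7 | equal variances | 0.85 | 86.6% | 80.8% | 85.8% |
| 0.9 | equal variances | 0.95 | 82.7% | 81.1% | 82.0% |
| 0.5 | truncated | 0.892 | 84.9% | 80.6% | 84.1% |
| 0.7 | truncated | 0.940 | 83.1% | 80.7% | 82.2% |
| 0.9 | truncated | 0.981 | 81.4% | 80.8% | 80.4% |

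The simulated difference runs from 89.5 − 80.3 = 9.2 points in favour of ANCOVA to 80.8 − 80.4 = 0.4 points against it.

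**Step 5: type I error when strata are omitted.** Under the null (r = 0.7, truncated baseline), with strata explaining 0%, 10% and 20% of change variance, the unadjusted t-test rejects in 5.1%, 4.0% and 3.1% of trials. ANCOVA with the strata rejects in 5.1%, 5.2% and 5.1%. With one perfectly balanced binary stratum the t-test figures are 5.0%, 3.7% and 2.7%, the same pattern.

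**The case against.** The strongest reply is that the plan is thin rather than silent. It defines a change score, names a two-group test for it, refers to two-sample t-tests again, and makes mixed models its approach to dropout. On that reading the analysis is a change-score t-test, a mixed model, or both, and what remains is a preference for ANCOVA over an unbiased and adequately powered method. This does not remove the gap: t-test and mixed model are different primary analyses, and no text chooses between them or gives the mixed model a treatment term at week 8.

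Several narrower points do stand:

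- The power gain is measured against the t-test. If a mixed model with a common baseline mean were primary, it would recover much of the same information and the gain could be near nil.
- ANCOVA's variance advantage is a large-sample statement. At r = 0.9 with truncation it loses a fraction of a point.
- The truncation case is stylised. The PANESS scale section suggests that children with NF1 may score worse than other groups. If the entry mean is a reference norm, fewer children are cut off and the result lies between the two halves of the table.
- Nothing in the documents supports any particular share of variance explained by the strata, and the resulting error is in the safe direction.
- The stepwise wording is attached to the association models. The plan does not propose it for the treatment comparison; it only fails to exclude it.
- Naming ANCOVA would not by itself settle the move to rank or bootstrap methods after data inspection, or the role of the 20% responder threshold.

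The statement that no primary model is written out covers the text available for review. A short part of the document directly after the Statistical analysis section was not available.

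**Conclusion.** The concern holds, as an improvement that costs nothing rather than a flaw in validity. The plan in view assigns no model, covariate set or week-8 contrast to the NAC-versus-placebo PANESS comparison, and its stratification factors are stated in two ways. This part does not depend on any assumed number.

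The efficiency part does. Relative to the change-score t-test at 26 per arm and d = 0.8, adjustment is worth about 9 points of power at r = 0.5 with equal variances. It is worth essentially nothing at r = 0.9 with a truncated baseline and strata that do not predict outcome. The case for changing the text therefore rests first on prespecification, with a possible power gain in addition.

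**What to change.** State one primary analysis: ANCOVA of week-8 PANESS on treatment, baseline PANESS and the stratification factors actually used (sex, ADHD, and age if it is a stratum). Then:

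- Make the two Randomization sections agree on age.
- Say what role the mixed models have for PANESS.
- State that stepwise selection is not used in any treatment comparison.
- Keep the change-score t-test as a supportive analysis.
- In the same paragraph, give the status of the rank or bootstrap fallback and of the 20% responder threshold.

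The cost is wording only. Every covariate is already collected and the sample size does not change. The model spends 3 of 50 degrees of freedom (baseline, sex, ADHD), or 4 with a single age term. In the least favourable scenario examined, the loss is under 1 point of power (80.8% to 80.4%).

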**Randomization:**

Following screening period, each participant will be sequentially assigned to one of the 2 treatment groups: NAC or placebo. This randomization will be stratified to ensure balance of sexes and ADHD between the intervention groups. Randomization will be implemented by the study statistician for this trial utilizing a permuted blocks approach. Password protection will be implemented to ensure that only certified clinical personnel are allowed to randomize patients and access the database. At the time of randomization, each participant will be assigned a unique medication kit identification number that will be used throughout the duration of the study.

**Statistical analysis:**

All analysis will be performed with SAS software version 9.4 (SAS Institute Inc., Cary, NC, USA). Spearman's correlation coefficient will be used to evaluate the univariate association between primary outcome (improvement of PANESS scores) and other neurophysiology and brain imaging measurements. Multivariate linear regression model will be used to assess the correlation between the outcomes and the risk factors adjusting for all possible confounders. Model selection criterions such as stepwise method will be employed when necessary. A p-value less than 0.05 will be considered statistically significant.

1. We will assess behavior vs. neurophysiology correlations:

- 1) two-month PANESS change ( $\text{PANESS}_{\text{post-NAC}} - \text{PANESS}_{\text{baseline}}$ ) vs. SICI change ( $\text{SICI}_{\text{post-NAC}} - \text{SICI}_{\text{baseline}}$ ).
- 2) two-month DuPaul change ( $\text{DuPaul}_{\text{post-NAC}} - \text{DuPaul}_{\text{baseline}}$ ) vs. SICI change ( $\text{SICI}_{\text{post-NAC}} - \text{SICI}_{\text{baseline}}$ ).
- 3) two-month BRIEF change ( $\text{BRIEF}_{\text{post-NAC}} - \text{BRIEF}_{\text{baseline}}$ ) vs. SICI change ( $\text{SICI}_{\text{post-NAC}} - \text{SICI}_{\text{baseline}}$ ). Paired t test comparisons of single pulse TMS responses (resulting from pTMS) will be performed to test whether, at each session, single pulse TMS responses differed. The mean single pulse TMS responses for each individual constitute the denominators for the SICI and ICF ratios and need to remain consistent for changes in SICI to be interpretable.

2. We will assess primary behavior (PANESS) vs. neuroimaging correlations:

- 1) two-month PANESS change ( $\text{PANESS}_{\text{post-NAC}} - \text{PANESS}_{\text{baseline}}$ ) vs. Fraction Anisotropy (FA) change ( $\text{FA}_{\text{post-NAC}} - \text{FA}_{\text{baseline}}$ ).

2) two-month PANESS change ( $\text{PANESS}_{\text{post-NAC}} - \text{PANESS}_{\text{baseline}}$ ) vs. MRS GSH change ( $\text{GSH}_{\text{post-NAC}} - \text{GSH}_{\text{baseline}}$ ).

3) two-month PANESS change ( $\text{PANESS}_{\text{post-NAC}} - \text{PANESS}_{\text{baseline}}$ ) vs. MRS GABA change ( $\text{GABA}_{\text{post-NAC}} - \text{GABA}_{\text{baseline}}$ ). The current HERMES method data analysis of MRS can observe GSH concentration changes in the brain of over 20%. We will determine if NAC dose changes GSH in brain and correlates with the primary outcome of study (PANESS).

For analyses of change over time, mixed models which include subject-specific random effects will be used to account for the correlation of multiple measurements on each subject and capture between-subject variation in rates of change. Unless otherwise noted, the Type I error rate for hypothesis tests and confidence intervals will be controlled at  $\alpha=0.05$ . To assist interpretation, the size of effects of interest in each model will be represented by  $R^2$  (proportion of outcome variation explained by predictors) for linear regression models and/or Cohen's  $d$  (difference in group means, in standard deviation units) for two sample t-tests [81].

Exploratory and descriptive data analysis will precede all inferential analyses to ensure that distributional assumptions are satisfied. In addition to computation of basic descriptive sample statistics (measures of central tendency, variability, and bivariate association), graphical tools such as histograms and scatterplots will be used to assess, e.g., approximate normality, linearity, and presence of influential outlying observations. If substantial violations of parametric assumptions are detected, we will implement non-parametric alternatives, including classical rank-based procedures as well as computationally-intensive sample re-use procedures such as the nonparametric bootstrap. Non-parametric procedures generally have less power than parametric procedures when the assumptions of the latter are met, but often have markedly better properties when the assumptions fail.

In the event that a participant is lost to follow-up, an incomplete series of observations can still be analyzed using the mixed-model methodology, provided that the dropout can be assumed to be missing at random in the sense that the probability that data are missing depends only on observed covariates (e.g., prior values of the outcomes, treatment assignment), rather than the unobserved values themselves. This assumption cannot be directly verified from the data. When it holds, however, mixed-model procedures yield the most efficient unbiased estimates, and implicitly impute the missing data using a subject-specific linear trend estimated from the non-missing observations. This effectively assumes that observed trends would have continued, in contrast to the "last observation carried forward" assumption that future observation would remain at a constant level equal to the last value. Neither assumption can be empirically proven correct. As a sensitivity analysis, therefore, the last available observation will be substituted for the protocol-defined last observation, provided that the participant had received at least one dose of study medication prior to the last observation. It is possible to determine whether participants who drop out are systematically different from those who do not with respect to observed data (e.g., baseline values, treatment assignment, demographic and clinical covariates). Logistic regression analyses will be used to explore whether such variables are predictive of dropout.

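### Where stepwise selection is used in the outcome/risk-factor regressions, the resulting p-values, intervals and R-squared are not valid at the stated 0.05 level, and no correction is planned

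*Combined protocol and SAP*

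**What the plan says.** All of this is in the Statistical analysis section of the combined protocol and SAP.

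- The model: "Multivariate linear regression model will be used to assess the correlation between the outcomes and the risk factors adjusting for all possible confounders".
- The selection rule: "Model selection criterions such as stepwise method will be employed when necessary".
- The threshold: "A p-value less than 0.05 will be considered statistically significant".
- The error rate: "Unless otherwise noted, the Type I error rate for hypothesis tests and confidence intervals will be controlled at" 0.05.
- The effect size for these models is R-squared, glossed as "proportion of outcome variation explained by predictors".

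The section does not list the candidate covariates, cap the model size, give entry or stay limits, name terms that must stay in, or say when selection becomes necessary. It plans no validation, shrinkage or optimism correction. A bootstrap is mentioned, but only as a fallback if parametric assumptions fail; it is not used to repeat or correct a selection step.

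**The concern.** Ordinary regression output assumes that the model was fixed before the data were seen. After stepwise selection, the terms on view are there because they looked strong in this sample. Their p-values are then too small, their intervals too narrow or off-centre, and R-squared too high. Because the trigger for selection is undefined, the decision to use it can also depend on the data.

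What is at stake is the evidence on associations. Developing predictive biomarkers is a stated purpose of the study, and several secondary aims relate TMS, MRI and MRS measures to clinical outcomes. A plan that says the type I error is controlled at 0.05 and reports uncorrected R-squared from selected models would make such associations look stronger and more certain than they are.

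**Working it through.** **1. Sample size available.** The Determination of sample size section says: "A sample size of 26 participants per group (52 in total) achieves 81% power to detect an effect size of 0.8 with significance level of" (the level stated there is 0.05). Check: a two-sided two-sample t-test with df = 50 and noncentrality 0.8 × √(26/2) = 0.8 × √13 = 2.88 has power 80.7%, which agrees with 81%. Enrolment: 52 / 0.90 = 57.8, so 58. The plan's figures reproduce, and n = 52 is right for change-score models that use both arms.

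**2. Assumptions.** The plan gives no figure for the regressions, so the number of candidates and the entry/stay limits are assumed. A simple count of named measures supports the range: SICI, ICF, FA, MD, RD, AD, GSH, GABA, ADHD-RS, BRIEF-2, TOVA and two WISC-V indices (13), plus age, sex, ADHD and IQ, make 17. Limits of 0.05 and 0.15 are used. In all simulations the outcome is pure noise and the candidates are independent normal variables.

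**3. Everything open to selection** (n = 52, forward-backward stepwise, 2,000 data sets per row):

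| Candidates | Entry/stay limit | At least one final p < 0.05 | Coverage of 95% intervals for selected terms | Mean R-squared when anything is selected |
|---|---|---|---|---|
| 5 | 0.05 | 23% | 0% | 0.121 |
| 5 | 0.15 | 26% | 61% | 0.098 |
| 10 | 0.05 | 39% | 0% | 0.138 |
| 10 | 0.15 | 47% | 56% | 0.136 |
| 15 | 0.05 | 54% | 0% | 0.155 |
| 15 | 0.15 | 66% | 50% | 0.180 |
| 20 | 0.05 | 64% | 0% | 0.173 |
| 20 | 0.15 | 79% | 46% | 0.233 |

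The 0% is by construction: with a stay limit of 0.05, a noise term survives only if its interval excludes the true value of 0. For R-squared, a single prespecified noise predictor has expectation 1/51 = 0.02.

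**4. How much of the false-predictor rate is due to selection?** Testing k independent noise predictors one at a time at 0.05 gives 1 − 0.95^k. A second set of simulations (n = 52, 500 data sets per setting) sets this beside stepwise:

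| Candidates | 1 − 0.95^k | One at a time, simulated | Stepwise, 0.05 | Stepwise, 0.15 |
|---|---|---|---|---|
| 8 | 34% | 33% | 33% | 39% |
| 12 | 46% | 45% | 45% | 53% |
| 16 | 56% | 55% | 55% | 67% |

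At 0.05 the rates are identical, because the first step admits a term only if some single-predictor test has p < 0.05. At 0.15 selection adds 6, 8 and 12 percentage points. Most of this rate is therefore multiplicity. Mean R-squared in the selected models was 0.12 to 0.19.

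**5. Term of interest forced in, only confounders selected** (2,000 data sets per setting; the forced term is a balanced two-group indicator). With 10, 15 and 20 null confounders, its type I error is 6.0%, 6.5% and 8.0% at limits of 0.05, and 7.0%, 8.5% and 10.1% at 0.15. With 8 to 16 confounders it is about 5% to 9%. Simulation standard error near 5% is √(0.05 × 0.95 / 2000) = 0.5 percentage points.

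**6. Sensitivity.**
- Candidates correlated at 0.3: false-predictor rate 29% to 50% (limit 0.05) and 41% to 72% (limit 0.15).
- Baseline models on 58 + 40 = 98 children: false-predictor rate 28% to 73%, mean spurious R-squared about 0.06 to 0.10.
- NAC arm only (about 26 children), if that is what the post-NAC change scores mean: mean spurious R-squared 0.23 to 0.39.

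**The case against.** The strongest reply is that the affected part of the plan is small. Stepwise is conditional and attached to one sentence about outcome/risk-factor regressions. The listed change-against-change analyses are pairwise, and Spearman correlation is named for associations with PANESS improvement; neither involves variable selection. The models are secondary analyses in a Phase II study meant to explore, and baseline biomarker models may draw on up to 98 children. If the factor of interest stays in the model, its type I error is only modestly inflated.

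All of this stands as a limit on scope and size. It does not remove the point. The plan does not say that the factor of interest is kept, it calls results significant at 0.05, and it says the error rate is controlled. An exploratory purpose would be an answer only if the selected models were labelled that way. The larger baseline sample reduces the R-squared inflation but hardly changes the false-predictor rate.

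A reader might infer more than the documents support:

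- **That stepwise could drop the treatment arm or undermine the efficacy result.** The plan never places arm in these regressions, and the arm comparison is sized on a two-sided t-test.
- **That stepwise itself causes the 30% to 70%.** Step 4 shows that most of it is multiplicity. Testing biomarkers one at a time without adjustment would leave it in place.
- **That Secondary Aim 5 builds on these selected models.** Nothing in the plan says so. That aim is exploratory and is also served by the 40-child single-visit cohort.

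**Conclusion.** The point holds for the outcome/risk-factor regressions, and only where stepwise selection is applied. There the nominal 0.05 level, the confidence intervals and R-squared cannot be taken at face value, and the plan has no safeguard. It is not a finding that every regression in the study is invalid: a model fitted without selection is outside it, as are the mixed models.

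The most direct effect is on R-squared and interval coverage. The effect on error rates depends on a choice the plan leaves open: modest if the factor of interest is always kept, large if every term competes for entry, and in the second case mainly because many candidates are examined. The sizes rest on the assumed candidate numbers, entry/stay limits and null data; other assumptions change the size but not the direction. The sample size of 52 evaluable and 58 enrolled is untouched.

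**What to change.** In the Statistical analysis section:

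1. Delete the stepwise sentence and the phrase "adjusting for all possible confounders".
2. For each outcome, prespecify a short covariate list: baseline value of the outcome, arm, and the randomisation factors sex and ADHD, plus age if it is a stratification factor. The two Randomization sections differ on age and should be reconciled. In models fitted on baseline data only, the arm and baseline-outcome terms do not apply.
3. Always keep the biomarker of interest in the model and test one biomarker at a time, with a stated multiplicity adjustment across biomarkers or an explicit exploratory label. With all five covariates and one biomarker, 52 children leave 52 − 7 = 45 residual degrees of freedom.
4. If a selected or multi-marker model is still reported, label it exploratory and give a cross-validated or bootstrap optimism-corrected R-squared, repeating the selection step in every fold or resample.

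The cost is SAP wording, with no change to sample size, visits or data collected. The downside is less favourable R-squared values and fewer nominally significant associations.
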